7.3.2. Analysis Methods for Total Daily Steps

7.3.2.1. Actual and Change from Baseline in Study Day *X* Total Daily Steps Prior to the Peak of a CAE

Among patients in the ankle accelerometry cohort who experienced a CAE, summary descriptive statistics of the actual TDS and change from baseline in TDS 1 day (eg, the 24-hour period on the day prior to the date of the CAE symptom peak) and at 3, 5, 7, 10, 14, and 21 days preceding the peak of a CAE will be presented for all CAEs and by moderate CAEs and severe CAEs.

In this analysis, among patients experiencing more than 1 CAE, the subsequent CAEs can be considered a separate CAE distinct from the first (preceding) CAE provided the patient exhibited at least 1 day of baseline albuterol use after the first (preceding) CAE's date of symptom peak and prior to the subsequent CAE's date of symptom peak. For patients who experience multiple CAEs (eg, 3), for a given number of days preceding a CAE (eg, 7 days), if the (eg, third) CAE overlaps with the time period of the preceding (eg, second) CAE, the CAE (eg, third CAE) should not be included in the analysis.

Among patients in the ankle accelerometry cohort summary descriptive statistics of the actual TDS and change from baseline in TDS will be presented for the first occurrence of a single day's albuterol use exceeding (i) 4 inhalations, (ii) 12 inhalations, and (iii) 20 inhalations, overall and by CAE status and by CAE severity.

In addition, summary descriptive statistics of the maximum change from baseline in TDS will be presented overall and by CAE status and by CAE severity. For patients who experienced a CAE, the maximum change from baseline in TDS is the maximum change from baseline in TDS among the days prior to the exacerbation.

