2.1.1. Justification of the Endpoints

The endpoints of the trial are the primary outcome measure (ie, CAE/severe CAE) and the primary outcome predictor (ie, albuterol use) alone or in combination with secondary predictors (ie, other study data). Multiple correlates of CAE focused on albuterol use, alone or in combination with other study data, will be modeled to determine which patterns best predict the subsequent development of CAE/severe CAE.

The increased use of SABA, deterioration in peak expiratory flow, and worsening of symptoms are associated with CAE in previously reported studies (Tattersfield et al 1999, Patel et al 2013b).

In the present trial, SABA use will be monitored electronically concomitant with the CAE event. Inspiratory flow values will be used as a surrogate for peak expiratory flow, because the study data require no additional patient effort and are also digital and concurrent. SDI is an effortless, digital concomitant correlate of sleep disruption, a key asthma symptom complex. Furthermore, TDS is an effortless, digital concomitant correlate of dyspnea on exertion, which is also a key symptom of asthma deterioration. These parameters therefore are likely to help predict the subsequent development of a moderate CAE or severe CAE.

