4.2.3. Inhalational Flow Values

The baseline inspiratory flow values are computed using the set of inhalations taken by the patient during study day 1 through day 14. Among these inhalations, the inhalation with the highest maximal inhalation flow (MIF) value is considered the ‘baseline inhalation’. The baseline MIF, inhalational volume, inhalation duration, and time to MIF values are those of the identified ‘baseline inhalation’. If no inhalations were taken during study day 1 through study day 14, the ‘baseline inhalation’ is the first available inhalation after study day 14.

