4.2.4. Total Daily Steps

Baseline TDS is the average number of daily steps a patient completes, computed using the daily steps recorded during the first 14 days of study participation (study day 1 through study day 14). The average will be calculated as the sum of the daily TDS divided by the number of days with nonmissing TDS. If no step data are available for study day 1 through study day 14, the ‘baseline TDS’ is the first available TDS after study day 14.

Baseline TDS are computed for those patients in the ankle accelerometry analysis set.

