7.1.1. Albuterol Use Definition

Baseline albuterol use is defined as no more than 4 inhalations (eg, 0 to 4 inhalations) per day of use regardless of the number of days albuterol is used in a 7-day period.

Daily baseline albuterol use is defined as no more than 4 inhalations (eg, 0 to 4 inhalations) per day.

Week 1 Patient Albuterol Use: Week 1 patient albuterol use is each patient's total number of albuterol inhalations taken and the number of days used during the first week (study day 1 through study day 7) of study participation with an indicator of whether or not any daily usage of albuterol exceeded 4 inhalations. It is presented as WK1:I#iD#dMT4Y/N, where "i" is the number of albuterol inhalations and "d" is the number of days used in the first 7 days of the study, and "MT4Y/N" is an indicator of whether or not any of the days albuterol was used exceeded 4 inhalations. For example, "I28D7MT4N" indicates a total of 28 inhalations were taken, albuterol use was used each day and none of the daily number of inhalations exceeded 4 (No More Than 4 inhalations per day Yes/ No).

Week 2 Patient Albuterol Use: Week 2 patient albuterol use is each patient's total number of albuterol inhalations taken and the number days used during the second week (study day 8 through study day 14) of study participation with an indicator of whether or not any daily usage of albuterol exceeded 4 inhalations. It is presented as "WK2:I#iD#dMT4Y/N", where "i" is the number of albuterol inhalations and "d" is the number of days used in the second week of study.

Albuterol use will be examined by the following 3 parameters; (i) total number of inhalations in the days preceding the peak of a CAE, (ii) number of days prior to the peak of a CAE when albuterol use increased, and (iii) number of albuterol uses in the day preceding a CAE.

The maximum number of inhalations taken within a 24-hour period by each patient: The date and time stamp of the inhalations are taken into consideration when determining the maximum number of inhalations taken within a 24-hour period by each patient. For patients who experienced a CAE, the maximum number of inhalations taken within a 24-hour period is determined among the days prior to the date of the symptom peak of the exacerbation.

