7.2.2. Analysis Methods for Inhalational Flow Values

7.2.2.1. Actual and Change from Baseline in Study Day *X* Inhalational Flow Values Prior to the Peak of a CAE

Among patients who experienced a CAE, summary descriptive statistics of the actual inhalational flow values and change from baseline in daily inhalational flow values for MIF, inhalational volume, inhalation duration, and time to MIF at 1 day (eg, the 24-hour period on the day prior to the date of the CAE symptom peak) and at 3, 5, 7, 10, 14, and 21 days preceding the peak of a CAE will be presented for all CAEs and by moderate CAEs and severe CAEs.

In this analysis, among patients experiencing more than 1 CAE, the subsequent CAEs can be considered a separate CAE distinct from the first (preceding) CAE provided the patient exhibited at least 1 day of baseline albuterol use after the first (preceding) CAE's date of symptom peak and prior to the subsequent CAE's date of symptom peak. For patients who experience multiple CAEs (eg, 3), for a given number of days preceding a CAE (eg, 7 days), if the (eg, third) CAE overlaps with the time period of the preceding (eg, second) CAE, the CAE (eg, third CAE) should not be included in the analysis.

Summary descriptive statistics of the actual inhalational flow values and change from baseline in daily inhalational flow values for MIF, inhalational volume, inhalation duration, and time to MIF will be presented for the first occurrence of a single day's albuterol use exceeding (i) 4 inhalations, (ii) 12 inhalations, and (iii) 20 inhalations, overall and by CAE status and by CAE severity.

In addition, summary descriptive statistics of the maximum change from baseline in daily inhalational flow values for MIF, inhalational volume, inhalation duration, and time to MIF will be presented overall and by CAE status and by CAE severity.

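### The maximum change in daily steps has no sign rule and, like maximum 24-hour inhalations, is compared between CAE groups over windows of unequal length

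*SAP*

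**What the plan says.** For steps, SAP 7.3.2.1 states that "summary descriptive statistics of the maximum change from baseline in TDS will be presented overall and by CAE status and by CAE severity". It then limits the window for one group only: for patients with a CAE, "the maximum change from baseline in TDS is the maximum change from baseline in TDS among the days prior to the exacerbation". Baseline TDS (SAP 4.2.4) is a mean, "computed using the daily steps recorded during the first 14 days of study participation".

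For flow, SAP 7.2.2.1 plans "summary descriptive statistics of the maximum change from baseline in daily inhalational flow values for MIF, inhalational volume, inhalation duration, and time to MIF", again by CAE status, with no window for either group. The flow baseline differs in kind. Among the inhalations of days 1 to 14, "the inhalation with the highest maximal inhalation flow (MIF) value is considered the" baseline inhalation, and all four parameters are read from it (SAP 4.2.3).

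For albuterol, SAP 7.1.1 says that in CAE patients "the maximum number of inhalations taken within a 24-hour period is determined among the days prior to the date of the symptom peak". SAP 7.1.2.5 reports this measure by CAE status. No limit is stated for patients without a CAE.

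On direction, Protocol 2.1.1 says that "TDS is an effortless, digital concomitant correlate of dyspnea on exertion, which is also a key symptom of asthma deterioration" and uses inspiratory flow in place of peak expiratory flow (PEF). Protocol 3.3 describes an earlier study of 425 severe exacerbations in which PEF fell before the event, with changes seen from 10 days beforehand.

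**The concern.** If steps and MIF worsen by falling, a signed maximum looks at the wrong tail: it reports the most active or best-flow day. The SAP does not say whether the maximum is signed, absolute or the largest fall, so two programmers could produce different tables from the same text.

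Separately, the expected extreme of a series grows with the number of days searched. Cutting the series at the event in CAE patients, with no cut in the others, gives patients without a CAE more extreme values even when the two groups behave alike. For albuterol, this works against the study hypothesis that use rises before a CAE.

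**Working it through.** **The plan's own figures.** The documents give no figure for these summaries. Their event figures reproduce: 360 × 0.20 = 72 and 360 × 0.25 = 90 CAEs. The same percentages applied to 90 to 100 ankle-accelerometer patients (100 planned, or 90 after 10% dropout) give 90 × 0.20 = 18 to 100 × 0.25 = 25 patients with a CAE.

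**Inputs from the documents.** Follow-up is 84 days (12 weeks). Baseline TDS is the mean of days 1 to 14. The CAE-patient window is the days before the event.

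**Assumptions.** Daily values are in within-patient SD units with lag-1 autocorrelation 0, 0.3 or 0.6. CAE day t is uniform on days 15 to 84. The fall is 0, 0.5, 1 or 2 SD over the 7 days before t. Patients without a CAE are searched over all 84 days. There are 40,000 simulated patients.

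**Statistic.** The change on day d is c(d) = y(d) − mean of y(1) to y(14). The signed maximum is the largest c(d) over days 1 to t − 1 (CAE) or days 1 to 84 (no CAE). The mean CAE window is (15 + 84)/2 − 1 = 48.5 days.

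**Window length alone, no deterioration.** At autocorrelation 0.3 the expected maximum is 1.26 SD over 7 days, 1.64 over 14, 1.97 over 28, 2.14 over 42 and 2.42 over 84. The difference between no CAE and CAE is:
- autocorrelation 0: 2.45 − 2.19 = 0.26
- autocorrelation 0.3: 2.42 − 2.15 = 0.27
- autocorrelation 0.6: 2.34 − 2.05 = 0.29

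**With a true fall before the CAE** (autocorrelation 0.3, SD units, CAE v no CAE where two values are given):

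| Fall | Signed maximum | Mean change, last 7 days (CAE) | Largest absolute change with its sign (CAE) | Largest decrease, unequal windows | Largest decrease, same 14 days |
|---|---|---|---|---|---|
| 0 | 2.15 v 2.42 | 0.00 | −0.01 | −2.16 v −2.42 | −1.64 v −1.64 |
| 0.5 | 2.11 v 2.42 | −0.49 | −0.45 | −2.28 v −2.42 | −1.93 v −1.64 |
| 1 | 2.10 v 2.42 | −0.97 | −1.01 | −2.50 v −2.42 | −2.31 v −1.64 |
| 2 | 2.12 v 2.42 | −1.94 | −2.58 | −3.24 v −2.42 | −3.21 v −1.64 |

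The signed maximum barely moves. The chance that the selected day lies in the 7 days before the CAE drops from 18% with no fall to 3% at 1 SD and about 0% at 2 SD. Correcting the sign alone is not enough: with a true 0.5 SD fall and unequal windows, patients without a CAE still show the larger decrease (−2.42 against −2.28). With a common 14-day window, the groups agree when nothing happens and separate when steps fall.

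**Flow.** The table does not transfer, because the flow baseline is a best value, not a mean. Two things can be said. A signed maximum for MIF over any window containing the baseline inhalation cannot be below 0. In a simple version of the same model, with baseline the best of days 1 to 14, ordinary days 15 to 84 average −1.48 to −1.70 SD with no deterioration.

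**Albuterol.** Assume identical use in both groups, mean 2 inhalations a day, the same windows, and calendar-day counts in place of 24-hour periods. The expected maximum is 5.7 (CAE) v 6.2 (no CAE) for Poisson counts. It is 10.3 v 11.9 for overdispersed counts (negative binomial with dispersion 1, variance 2 + 2²/1 = 6).

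**The case against.** The strongest reply is that the SAP never says the maximum is signed. Read as the largest absolute change with its sign kept, the statistic does respond to a fall, as the table shows. That stands. A reader might infer that the rule certainly picks each patient's best day, but the text supports only an undefined direction that fails if taken literally. The unequal windows remain under any reading.

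A reader might also infer unequal windows for flow. SAP 7.2.2.1 states no window for either group, so that is not documented. Even for TDS and albuterol, the full-study window in patients without a CAE is inferred from the absence of a limit.

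Nor does a best-day reading fit all four flow parameters. SAP 7.5.2.1 takes the weekly minimum of time to MIF alongside the maximum of MIF and volume, which suggests that a longer time is worse; a signed maximum would then point the right way. No direction is given for inhalation duration. That steps fall is implied by the link to dyspnea rather than stated.

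Last, a reader might conclude that the plan cannot show deterioration before a CAE. It can. SAP 7.2.2.1 and 7.3.2.1 give values and changes at 1 to 21 days before the peak, weekly summaries follow, and for flow SAP 7.5.2.1 tests a paired comparison of the two weeks before onset. These do not fully replace the statistic for steps: the pre-peak values cover CAE patients only, weekly values follow study weeks, and the paired-week analysis omits TDS.

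For albuterol, the maximum is already the deteriorating direction, and excluding use after the peak is sensible. Only the missing matching limit in the other group is at fault.

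**Conclusion.** The point holds for specific descriptive summaries. For TDS, the direction is undefined, and a literal reading is almost blind to a pre-CAE fall. The same wording is a problem for MIF and probably for inhalational volume. For TDS and for maximum 24-hour inhalations, the stated rule limits only CAE patients, so window length alone makes patients without a CAE look more extreme. The size is about 0.25 to 0.3 SD for TDS. For albuterol it is 6.2 − 5.7 = 0.5 to 11.9 − 10.3 = 1.6 inhalations. These sizes rest on the assumed CAE timing, the 84-day window for patients without a CAE and, for albuterol, the assumed mean and dispersion. The direction of the bias does not depend on those values, provided patients without a CAE are searched over more days. No hypothesis test or sample size uses these summaries, and the other pre-peak and weekly summaries are unaffected.

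**What to change.** Amend SAP 7.2.2.1 and 7.3.2.1 to replace the maximum change with the largest decrease from baseline for TDS, MIF and inhalational volume, and the largest increase for time to MIF. State the direction for inhalation duration.

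Take every such extreme over the same fixed-length window in both groups, and apply this to 7.1.2.5 as well. One choice is the 14 days before the symptom peak in CAE patients and matched study days in patients without a CAE. Fourteen days covers the changes that Protocol 3.3 notes from 10 days before an event; a 7-day window would not. Say how CAEs in the first 14 days are handled, since they overlap the baseline period and may lack a full window.

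The cost is SAP wording and reprogramming of a few tables before database lock, with no new data. The small downside is that days outside the window are not used.

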7.3.2.2. Actual and Change from Baseline in Week *Y* Total Daily Steps

Summary descriptive statistics of the actual Week *Y* TDS and change from baseline in TDS for each study week (1 through 12) will be presented overall, and by CAE status and by CAE severity (Yes: severe, moderate; No) using the ankle accelerometry analysis set.

7.4. Accelerometry: Sleep Disruption Index

7.4.1. Sleep Disruption Index Definition

The sleep disruption index (SDI) for analysis in this study will consist of the following measures, which correlate significantly with SABA rescue use (Krouse et al. 2008) and the composite score derived from the summation of these 3 measures.

- (i) Nighttime Average Sleep Latency Time ($r=0.78$)
- (ii) Longest Nighttime Wake Episode ($r=0.73$)
- (iii) Total Time Awake at Night ($r=0.65$)

Study Day X and Week Y SDI are defined as follows:

Study Day X Nighttime Average Sleep Latency Time: The nighttime average sleep latency time for Study Day X is the nighttime average sleep latency time recorded by wrist accelerometry on Study Day X .

Week Y Nighttime Average Sleep Latency Time: The nighttime average sleep latency time for Week Y is computed using the set of nighttime average sleep latency times recorded by wrist accelerometry during a given week on study. The average will be calculated as the sum of the daily nighttime average sleep latency times divided by the number of days with nonmissing nighttime average sleep latency times.

Study Day X Longest Nighttime Wake Episode: The longest nighttime wake episode for Study Day X is the longest nighttime wake episode calculated as described in Section 4.2.5 on Study Day X .

Week Y Longest Nighttime Wake Episode: The longest nighttime wake episode for Week Y is the greatest longest nighttime wake episode calculated as described in Section 4.2.5 during a given week on study.

Study Day X Total Time Awake at Night: The total time awake at night for Study Day X is the total time awake at night time recorded by wrist accelerometry on Study Day X

Week Y Total Time Awake at Night: The total time awake at night for Week Y is computed using the set of total time awake at night times recorded by wrist accelerometry during a given week on study. The average will be calculated as the sum of the total time awake at night times divided by the number of days with nonmissing total time awake at night times.

Study Day X SDI Composite Score: The SDI composite score for Study Day X is sum of nighttime average sleep latency time, longest nighttime wake episode and total time awake at night on Study Day X .

Week Y SDI Composite Score: The SDI composite score for Week Y is the sum of nighttime average sleep latency time, longest nighttime wake episode and total time awake at night for Week Y .

The SDI are computed for those patients in the wrist accelerometry analysis set.

7.4.2. Analysis Methods for Sleep Disruption Indices

7.4.2.1. Actual and Change from Baseline in Study Day X Sleep Disruption Indices Prior to the Peak of a CAE

Among patients in the wrist accelerometry cohort who experienced a CAE, summary descriptive statistics of nighttime average sleep latency time, longest nighttime wake episode, and total time awake at night and change from baseline in these three measures of SDI at 1 day (eg, the 24-hour period on the day prior to the date of the CAE symptom peak) and at 3, 5, 7, 10, 14 and 21 days preceding the peak of a CAE will be presented for all CAEs and by moderate CAEs and severe CAEs.

Summary descriptive statistics of nighttime average sleep latency time, longest nighttime wake episode, and total time awake at night and change from baseline in these three measures of SDI will be presented for the first occurrence of a single day's albuterol use exceeding (i) 4 inhalations, (ii) 12 inhalations, and (iii) 20 inhalations overall, and by CAE status and by CAE severity.

In addition, summary descriptive statistics of the maximum daily change from baseline nighttime average sleep latency time, longest nighttime wake episode, and total time awake at night will be presented overall and by CAE status and by CAE severity.

7.4.2.2. Actual and Change from Baseline in Week Y Sleep Disruption Indices

Summary descriptive statistics of the absolute Week Y nighttime average sleep latency time, longest nighttime wake episode, total time awake at night, and SDI composite score and change from baseline in these four sleep disruption indices for each study week (1 through 12) will be presented overall, and by CAE status and by CAE severity.

7.5. Clinical Asthma Exacerbation

7.5.1. Clinical Asthma Exacerbation Definition

A CAE is the primary outcome measure of this study. In this study, a CAE is an occurrence of either a "severe CAE" or a "moderate CAE." defined as the following:

- A severe CAE is defined as a CAE that involves worsening asthma such that
 - the treating physician elects to administer prednisone (or equivalent glucocorticoid treatment) at least 10 mg prednisone equivalent above baseline (Table 2), for at least 3 daysAND
 - an unscheduled provider visit such as an office visit, urgent care visit, emergency care visit, or hospitalization
- A moderate CAE is defined as a CAE that involves worsening asthma such that
 - the treating physician elects to administer prednisone (or equivalent glucocorticoid treatment) at least 10 mg prednisone equivalent above baseline (Table 2), for at least 3 days

OR

- an unscheduled provider visit such as an office visit, urgent care visit, emergency care visit, or hospitalization associated with an increase in asthma therapy that does not qualify for “severe CAE” as defined above

Table 2: Systemic Glucocorticoid Treatment Equivalent to 10 mg of Prednisone

Glucocorticoid Treatment	Dose (mg) Equivalent to 10 mg of Prednisone	Comment
Cortisone	50	Includes parenteral
Hydrocortisone	40	Cortisol
Prednisolone	10	-
Methylprednisolone	8	Medrol: includes parenteral SOLU-MEDROL®
Triamcinolone	8	-
Betamethasone	0.4	-
Dexamethasone	0.4	Oral or parenteral DECADRON®

The designation of a CAE as moderate or severe is denoted by the response to the CRF question “Severity” on the Clinical Asthma Exacerbation CRF page regardless of whether the following CRF questions are answered in the negative or missing:

- “The treating physician elects to administer prednisone (or equivalent glucocorticoid treatment) at least 10 mg prednisone equivalent above baseline, for at least 3 days”
- An unscheduled provider visit such as an office visit, urgent care visit, emergency care visit, or hospitalization

A patient may experience more than 1 CAE during the study period.

Clinical Asthma Exacerbation Status: Clinical asthma exacerbation status is an indicator of whether or not a patient experienced a CAE during study follow-up (Yes, No).

Clinical Asthma Exacerbation Rate: The percentage of patients who experience at least 1 moderate or severe CAE at the end of study follow-up.

Recurrent Clinical Asthma Exacerbation Rate: The percentage of patients who experience more than 1 moderate or severe CAE at the end of study follow-up.

Time to Clinical Asthma Exacerbation: Time, in days, from Study Day 1 to the Date of Symptom Peak plus 1.

